#### Tumor assessments

- Tumor assessments will be performed using RECIST 1.1. (Appendix I) Investigator determined response assessments will be performed at each assessment time point and entered onto the eCRF. Copies of all tumor imaging studies will be sent to an imaging core laboratory (Central Review) for prospective on-study primary efficacy assessment. Tumor assessments will be carried out following the guidelines provided by the study sponsor. Tumor assessments (CT of abdomen, and pelvis, and of all other known sites of disease) will be performed during the screening phase and, the first assessment will be performed 6 weeks after the first dose, the second assessment will be performed 12 weeks after the first dose, then every 12 weeks during study treatment cycles in the treatment phase or sooner if clinically indicated until documentation of disease progression.
- A brain CT/MRI will be performed at screening, as clinically indicated. In addition, for subjects with history of treated brain metastases, brain scans must be performed at screening and every tumor assessment time point.

- Page 38 of 88 Date: April 04th, 2016
- Data from somatostatin receptor schintigraphy or PET-CT (octreoscan) with specific radiolabeled agents for neuroendocrine tumors (such as Ga68, 5-HTP or F-Dopa) will be collected if available and performed within the 6 months prior to the first dose of study drug but are not acceptable as tumor assessment techniques during treatment phase.
- Data from bone scan will be collected, if available and performed within 6 months prior
  to first dose of study drug and every 24 weeks after first dose of study drug, and at the
  final visit unless the last scan was performed less than 24 weeks before.
- Somatostatin schintigraphy, PET and bone scan are not compulsory. They will be collected, if performed.
- A chest x-ray or skeletal x-ray that clearly demonstrates a new metastatic lesion may be used to document progression in lieu of the CT/MRI scans.
- Subjects who discontinue study drug prior to disease progression must continue to undergo tumor assessments every 12 weeks in the follow-up period, until disease progression is documented or another anti-cancer therapy is initiated.

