### 13.2.2 Treatment phase assessments schedule

### 13.3 Treatment cycle procedures

Efforts should be made to conduct study visits on the day scheduled (window  $\pm$  1 day). Clinical laboratory assessments may be conducted anytime within 72 hours prior to the scheduled visit, unless otherwise specified in the Schedule of Visits and Procedures. Whenever possible, subjects should be evaluated at approximately the same time of the day (e.g., morning or afternoon) at each visit, and reasonable efforts should be made to conduct all evaluations in the same test order at each visit.

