4.2 Secondary objective(s) and secondary variables

The secondary objectives are:

- To determine the safety and tolerability of lenvatinib.
- To estimate the early tumor shrinkage rate and the deepness of response of lenvatinib in each cohort of patients.
- To estimate progression-free survival in both cohorts of patients.

Secondary variables:

- To determine the safety and tolerability of lenvatinib. Safety will be assessed by adverse events (AEs) and serious adverse events (SAEs). Echocardiogram results (LVEF reductions) and QTc (using the QTcB and QTcF values) prolongations will be examined. QTc prolongation will be examined through the adverse events.
- To estimate the early tumor shrinkage (ETS) rate and the deepness of response
 (DpR) of lenvatinib in each cohort of patients:
 - ETS rate is defined as 20% reduction in target lesions after the first 6 weeks of treatment (first tumor assessment).
 - DpR is defined as percentage of maximum tumor shrinkage observed at the nadir (minimum value of total sum of diameters) compared with baseline.

To assess ETS and DpR, total sum of diameters obtained in all tumor assessments will be considered.

• To estimate progression-free survival (PFS) in both cohorts of patients. PFS is defined as the time from the date of treatment start (C1D1) to the date of first documentation of disease progression or death (whichever occurs first) using RECIST 1.1.

Page 9 of 16 Date: June 04, 2020

To evaluate PFS, it will be considered:

- Start date of study drug
- o Progression disease date or death date (whichever comes first)

PFS censoring rules will follow FDA guidance in 2007 [1]:

Table A. PFS 1 (includes documented progression only)

Situation	Date of Progression or Censoring	Outcome
No baseline tumor assessments	Randomization	Censored
Progression documented between scheduled	Earliest of:	Progressed
visits	 Date of radiological assessment showing new lesion (if progression is based on new lesion); or Date of last radiological assessment of measured lesions (if progression is based on 	
	increase in sum of measured lesions)	6 1
No progression	Date of last radiological assessment of measured lesions	Censored
Treatment discontinuation for undocumented progression	Date of last radiological assessment of measured lesions	Censored
Treatment discontinuation for toxicity or other reason	Date of last radiological assessment of measured lesions	Censored

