New anticancer treatment started	Date of last radiological assessment of measured lesions	Censored
Death before first PD assessment	Date of death	Progressed
Death between adequate assessment visits	Date of death	Progressed
Death or progression after more than one missed visit	Date of last radiological assessment of measured lesions	Censored

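### SAP Table A gives opposite PFS outcomes for a death after both the week-6 and week-12 scans are missed, and does not define a missed visit

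*SAP*

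**What the plan says.** SAP 4.2 gives the definition: "PFS is defined as the time from the date of treatment start (C1D1) to the date of first documentation of disease progression or death". The earlier of the two counts, and no exception is made for missed scans. Table A then assigns dates and outcomes. Three of its rows matter here:

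- "Death before first PD assessment": progressed, at the date of death.
- "Death between adequate assessment visits": progressed, at the date of death.
- "Death or progression after more than one missed visit": censored, at the "Date of last radiological assessment of measured lesions".

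The scan schedule is in Protocol 12.2: "the first assessment will be performed 6 weeks after the first dose, the second assessment will be performed 12 weeks after the first dose". Later scans follow at 12-week intervals. The screening scan falls within the 28 days before C1D1 (Protocol Table 4, note j). SAP 6.2.1 reports PFS as a Kaplan-Meier median with a 95% confidence interval, on the Full Analysis Set and the Per Protocol Set. SAP 6.10 (derived variables) and 6.11 (missing data) give no order among the Table A rows. Protocol 12.3 and SAP 4.2 both cite a 2007 FDA guidance as the source of the rules.

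**The concern.** Two rows of one table can apply to the same death and give opposite results. One of them removes a death that the PFS definition counts, and it does so at a date before the PFS clock starts. Whoever programs the endpoint would settle the outcome by the order in which the rows are coded.

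The trigger for the censoring row is also undefined. The SAP does not say whether a missed visit is a missed scan or a missed clinic attendance, or whether the misses must be consecutive.

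PFS is a stated secondary objective. It also feeds the biochemical-response analysis (SAP 6.3) and ten subgroup variables (SAP 6.4). There is no control arm in which a bias in the absolute estimate could cancel. A patient too ill to be scanned twice who then dies plausibly has a worse prognosis than the rest, so censoring would push PFS upward.

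**Working it through.** **1. The plan's own figure.** The plan gives no PFS assumption, event count or power. Its only design figure is 55 per cohort for ORR (Protocol 20.6: 10% against 25%, 90% power, 5% level). An exact single-stage binomial design reproduces it: with n = 55 and success at 10 or more responses, the one-sided error is 0.044 and power is 0.911. Nothing below changes that figure.

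**2. One patient, two rows, reading visit as scan.** The week-6 and week-12 scans are missed and death occurs in week 14.

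- "Death before first PD assessment" applies because no post-baseline assessment took place: event at week 14.
- "Death or progression after more than one missed visit" applies because two scans were missed: censored at the last scan, which is the screening scan. That scan precedes C1D1 by up to 28 days, so PFS time is negative, or zero if truncated. No floor is stated.

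**3. Who is caught on the scan reading.** Take deaths with no post-baseline scan:

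| Time of death | Scheduled scans missed | Rows met |
|---|---|---|
| Before week 6 | 0 | Death row only: event |
| Week 6 to week 12 | 1 | Death row only: event |
| After week 12 | 2 or more | Both: event or censored |

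Only the last line conflicts. These patients matter in the Full Analysis Set alone, because the Per Protocol Set requires a post-baseline tumor assessment.

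**4. The clinic-visit reading.** Protocol 13.3 uses the word for scheduled attendances ("Efforts should be made to conduct study visits on the day scheduled"), and Protocol Table 5 separates treatment visits with a tumor assessment from those without. From cycle 4 attendances are 4-weekly (28-day cycles, Day 1) while scans are 12-weekly, so weeks 16 and 20 fall between the week-12 and week-24 scans.

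- A patient scanned on time at weeks 6 and 12 who misses the week-16 and week-20 attendances and progresses on the scheduled week-24 scan would be censored at week 12, taking the last scan before the gap. No scan was missed. On the scan reading this is an event.
- A patient who misses the Day 7 and Day 15 attendances of cycle 1 and dies in week 3 would meet both rows before any scan was due.
- The week-14 patient in step 2, if seen at clinic throughout, would meet the death row only.

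**5. Size.** Assumptions, not in the documents: six-month PFS is 60% when every death counts, that is 33 of 55 event-free with no other censoring, and k of the 22 events are deaths of the kind in step 2. Censoring these at time zero removes them from the risk set, so

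reported PFS = 0.60 / (1 − k/55) = 33 / (55 − k).

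- k = 0: 33/55 = 60.0%
- k = 1: 33/54 = 61.1%
- k = 2: 33/53 = 62.3%
- k = 3: 33/52 = 63.5%

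For the median, assume exponential PFS with a 12-month median when these deaths are censored. Counting them as early events, the median solves (1 − k/55) × S(t) = 0.5, so t = −12 × ln[0.5 / (1 − k/55)] / ln 2. This gives 12.0 months for k = 0, 11.7 for k = 1 and 11.0 for k = 3.

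**The case against.** **The table's context favours scans.** The adjacent row reads "Death between adequate assessment visits", another row dates progression found between visits by a radiological assessment, and the disputed row itself censors at a radiological date. This stands. A reader might infer from the protocol's usage that missed visit means clinic attendance, so that progressions after two missed attendances are routinely censored. The documents do not support that as the intended rule. They support only that the term is undefined and open to that reading.

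**The overlap may not be intended.** If the death row meant death before the week-6 scan was due, the two rows would not overlap on the scan reading. The SAP does not say so, and the disputed death would then be censored before C1D1.

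**The rules come from a cited guidance.** Censoring after a long gap can be a deliberate convention, and that stands. Whether the source settles precedence cannot be checked here. The SAP's table is what will be programmed, and it was not fully adapted: its first row dates censoring from randomization, while Protocol section 6 says there is none.

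**A third row may apply.** A patient this ill may have stopped treatment, and Table A has censoring rows for discontinuation. This is correct, and it adds to the need for a stated order.

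**The effect is small.** At n = 55 the 95% half-width around 60% is about 1.96 × √(0.6 × 0.4 / 55) = 0.129, or 13 points, against a shift of at most 3.5 points in the range assumed. PFS is estimated, not tested against a threshold. This stands and limits the weight of the point.

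**Conclusion.** The contradiction is real but narrow. A death after both the week-6 and week-12 scans are missed is an event under one row and censored under another at a date before C1D1. No precedence is stated, and the PFS definition sides with the event. The undefined term is a second, separate ambiguity.

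On the scan reading, which the table favours, only deaths after week 12 with no post-baseline scan are affected. Their number cannot be known from the documents and may be zero. With 0 to 3 of 55 assumed, a 60% six-month PFS would be reported as 60% to 63.5%.

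A reader might go further and infer that median PFS is inflated in both cohorts, that all early deaths are at risk, or that toxicity interruptions feed the problem. The documents do not support these. Nothing shows that such a patient exists in either cohort. Deaths before week 12 meet the event row alone. Scans run from the first dose and continue after the drug is stopped (Protocol 7.3 and 12.2), so an interruption does not itself cause a missed scan. The primary ORR and the sample size are unaffected.

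**What to change.** In SAP 4.2, Table A:

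1. Replace the missed-visit wording with two or more consecutive missed scheduled tumor assessments.
2. State that a death with no post-baseline scan is an event at the date of death, so that "Death before first PD assessment" takes precedence. Say in the same sentence how this sits with the discontinuation and new-treatment rows.
3. Set every censoring date no earlier than C1D1. This also covers a living patient with no post-baseline scan, who is otherwise censored at the screening scan. Replace randomization with C1D1 in the first row.
4. Add one sensitivity Kaplan-Meier analysis per cohort that counts every documented progression or death as an event, regardless of missed scans.

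The cost is a few lines of SAP text and one extra run. Reported PFS may be slightly shorter.

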4.3 Exploratory objective(s) and variables

The exploratory objectives are:

- To evaluate biochemical response (changes in CgA, 5-HIAA and NSE levels) and its association with response rate and progression-free survival.
- To assess whether baseline tumor and blood biomarkers may be predictive of response to lenvatinib.
- To explore additional hypotheses related to biomarkers and relationship to lenvatinib, neuroendocrine tumors, other endocrine disorders and/or cancer which may arise from internal or external research activities.

Exploratory variables:

- The changes in tumor markers (CgA, 5-HIIAA and NSE) will be analysed by cohort and significant reductions defined as 50% reduction or more regarding the baseline values will be calculated.
- The relationship between reductions and PFS and radiological response will be assessed.

EudraCT number: 2015-001467-39

Confidential Version 2.0

Page 10 of 16 Date: June 04, 2020

The second and third exploratory objectives will be assessed in the final analysis not in the interim analysis. According to the biomarkers that are available, the analysis of these objectives will be specified.

5. Study populations

The analysis sets will be defined as follows:

- Full Analysis Set will include all allocated subjects. This will be primary analysis set for the efficacy endpoints.
- Per Protocol Analysis Set will include those subjects who were allocated and received at least one dose of the assigned study drug and had no major protocol deviations. The subjects will complete both baseline and at least one post-baseline tumor assessments (week 6). Experior will send a list of major protocol deviations to establish the per-protocol set after the close out of data base. The PI ([name]) will decide which patients should be excluded to define the per protocol analysis set.
- Safety Analysis Set will include all subjects who were allocated and received at least one dose of the study drug and had at least one post-baseline safety evaluation (week 6). This will be the analysis set for all safety evaluations.

6. Statistical strategy

Below are detailed the statistical aspects of the data analysis.

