6.1 Primary analysis

All efficacy analyses will be based primarily on the Full Analysis Set and secondarily on the Per Protocol Analysis Set.

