6.2 Secondary analysis

The secondary analysis will be based on the Full Analysis Set and the Safety Analysis Set.

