6.2.1 Summary statistics

Secondary endpoints will be summarized with descriptive statistics. Continuous variables will be summarized with n, NA, mean, standard deviation, median and range. Frequency counts and percentage of subjects within each category will be provided for categorical data.

First secondary objective:

Safety analyses will be based on the Safety Analysis Set. All safety analyses will be summarized separately by cohort.

Adverse events will be classified into standardized medical terminology from the verbatim description (investigator term) using the Medical Dictionary for Regulatory Activities (MedDRA). Adverse events will be presented by preferred term (PT) and by system organ class (SOC).

Echocardiogram results (LVEF), and their changes from baseline will be summarized using descriptive statistics. Prolongation of QTc will be analysed using descriptive statistics and frequency tables.

The degree of exposure (dose, duration of treatment, interruptions/reductions of dose) will be assessed to determine the degree to which study safety can be assessed. These results will be presented with descriptive statistics (n, NA, mean, standard deviation, median and range).

Second secondary objective:

The ETS and DpR will be calculated for each cohort. Both ratios will be calculated using the total sum of diameters provided in tumor assessments by central radiology review.

Third secondary objective:

PFS will be calculated using start date of study drug and progression disease or death date (whichever occurs first), based on the Full Analysis set and Per-protocol Analysis Set. PFS censoring rules will follow FDA guidance in 2007 (see Table A).

OS will be calculated using start date of study (C1D1).

A Kaplan Meier survival analysis will be carried out to analyse PFS, providing the median and the corresponding 95% CI of time to progression. Survival curves will be reported.

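### The per-protocol set requires a post-baseline scan but is used for ORR and for PFS from C1D1, so unscanned patients, including early deaths, are excluded and those supportive results can only rise through it

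*SAP*

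**What the plan says.** SAP section 5 restricts the per-protocol set to allocated, dosed patients without major deviations and adds: "The subjects will complete both baseline and at least one post-baseline tumor assessments (week 6"). Protocol 20.2 has the same condition. The Full Analysis Set, by contrast, "will include all allocated subjects. This will be primary analysis set for the efficacy endpoints".

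On use, SAP 6.1 states: "All efficacy analyses will be based primarily on the Full Analysis Set and secondarily on the Per Protocol Analysis Set". For PFS, SAP 6.2.1 repeats that the analysis is "based on the Full Analysis set and Per-protocol Analysis Set". SAP 6.2, which introduces the same analyses, names different sets: "The secondary analysis will be based on the Full Analysis Set and the Safety Analysis Set".

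On the endpoint, SAP 4.2 says: "PFS is defined as the time from the date of treatment start (C1D1) to the date of first documentation of disease progression or death". Table A in that section treats "Death before first PD assessment" as an event on the date of death. It censors "Treatment discontinuation for toxicity or other reason" at the last radiological assessment. ORR (SAP 4.1) is CR plus PR divided by the total of patients.

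Two other provisions bear on the same patients. Protocol 20.7 admits patients who are lost or stop treatment to the primary endpoint analysis only if they have at least one tumor assessment. SAP 6.11 plans no imputation and works with the available data.

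**The concern.** Membership of the set depends on an event after time zero, while PFS is counted from time zero. Dying before the first scan is an outcome, not a protocol deviation, and major deviations already have their own clause in the definition. The scan condition therefore adds only selection on what happened to the patient. The Table A row for death before the first assessment has nothing to act on in this set when no scan was done.

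At stake is what the per-protocol results can be used for. If they look the same as, or better than, the Full Analysis Set results, part of the reason may be that patients who did badly early were left out.

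The wording is also unclear. Read strictly, the week-6 parenthesis drops a patient whose only post-baseline scan came earlier, for example an unscheduled scan showing progression, or only at week 12.

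**Working it through.** **Inputs.** N = 55 per cohort, with ORR of 10% unacceptable and 25% of interest, 5% level and 90% power (protocol 20.6). PFS origin and Table A come from SAP 4.2, and the ORR definition from SAP 4.1. The number k of patients without a post-baseline scan is not given and is assumed. The PFS median of 10 months and the exponential shape are also assumed.

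**The plan's own figure.** The smallest exact one-sided single-stage design with P(X ≥ r | 0.10) ≤ 0.05 and P(X ≥ r | 0.25) ≥ 0.90 is n = 55 with r = 10 (alpha 0.0444, power 0.911). So 55 reproduces and serves as the denominator below.

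**ORR.** An unscanned patient cannot be a responder, so excluding k of them changes R/55 to R/(55 − k), a factor of 55/(55 − k). The design rate gives 0.25 × 55 = 13.75, so take R = 14:

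| k | Full set | Per-protocol |
|---|---|---|
| 1 | 14/55 = 25.5% | 14/54 = 25.9% |
| 3 | 25.5% | 14/52 = 26.9% |
| 5 | 25.5% | 14/50 = 28.0% |

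**PFS: who moves the curve.**
- A patient who dies unscanned is an event in the full set and absent from the per-protocol set. The curve rises.
- A patient who stops unscanned for toxicity or undocumented progression is censored under Table A at the last scan. That is the baseline scan, at or before C1D1. Such a patient contributes no time at risk, so exclusion leaves the Kaplan-Meier curve unchanged.
- A patient with progression on a scan before week 6 is an event. This patient is lost only if the week-6 parenthesis is read strictly.

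**PFS: size, unscanned deaths only.** With d = k/55, S_PP(t) = S(t)/(1 − d) after week 6. The per-protocol median solves S(t) = 0.5(1 − d). For an exponential curve with median m this gives m × [1 + log2(1/(1 − d))].
- k = 1: 10 × [1 + log2(55/54)] = 10 × 1.026, about 10.3 months.
- k = 2: 10 × [1 + log2(55/53)] = 10 × 1.053, about 10.5 months.

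**Ceiling on k in this model.** Six weeks is about 1.38 months, so the share of all PFS events by then is 1 − 2^(−1.38/10) = 9.1%, or 0.091 × 55 ≈ 5 patients. That share includes progressions as well as deaths, so unscanned deaths cannot exceed it.

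**Direction.** For unscanned patients it is fixed: the ORR numerator is untouched while its denominator shrinks, and the only PFS contributions removed are early events or nothing. It is not fixed for a patient first scanned at week 12 and dropped on the strict reading, because that patient may be a responder.

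**The case against.** The strongest reply is that the set is only supportive. The Full Analysis Set is primary for efficacy and keeps these patients and the early-death row of Table A. No decision rule uses the per-protocol set, SAP 6.1.2 plans no inference on ORR, and both sets will be reported, so any difference will be visible. The SAP also does not say that agreement between the sets is meant to reassure. All of this stands and limits the weight of the point. It does not explain why a deviation-based set should also be selected on a post-treatment scan.

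A reader might infer that every failure before week 6 is removed by definition, or that no member can die in the first six weeks. The documents do not support that. Under protocol 7.3, patients who stop the drug before progression stay on the scan schedule and can enter the set. Protocol 12.2 allows earlier scans when clinically indicated, and such a scan is a post-baseline assessment unless the parenthesis is read strictly.

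A reader might also infer that per-protocol PFS is materially inflated, for instance by assuming that 10% of a cohort is lost before the first scan. That would exceed all the PFS events (9.1%) that a 10-month exponential model allows by week 6. It would also count patients who are merely censored at baseline. Eligibility is limited to G1/G2 disease and ECOG 0–1, and no early death rate is given, so the number of unscanned deaths may be zero.

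Finally, excluding major deviators can move the per-protocol results either way, so the net difference from the full set is not fixed. This limits the upward-only statement to the scan condition.

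**Conclusion.** The point holds for supportive results. The scan condition excludes deaths before any post-baseline scan from per-protocol PFS, and all unscanned patients from per-protocol ORR. Through those exclusions both results can only move upward. The effect is small if few patients are unscanned: 0.4 to 2.5 percentage points on an ORR of 25.5% for 1 to 5 of 55, and about 0.3 to 0.5 months on a 10-month median for one or two unscanned deaths. These counts, the median and the exponential shape are assumptions. If every patient is scanned at week 6, there is no effect.

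The Full Analysis Set as defined is not affected. Protocol 20.7 with SAP 6.11, however, can be read as bringing a similar selection into the primary ORR, in conflict with a set of all allocated subjects. That conflict could matter more than the per-protocol wording and should be settled with it.

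**What to change.** In SAP section 5 and protocol 20.2, delete the post-baseline scan condition. The per-protocol set then consists of allocated, dosed patients with a baseline tumor assessment and no major deviation. Within it, count patients without a post-baseline scan as non-responders for ORR and apply Table A to their PFS. If a response-evaluable set is wanted, define it separately, name it as such and use it for ORR only.

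At the same time:
- Reconcile SAP 6.2 (Full Analysis and Safety sets) with SAP 6.2.1 (Full Analysis and per-protocol sets for PFS).
- Reconcile protocol 20.7 and SAP 6.11 with the Full Analysis Set definition, stating that unscanned patients remain in the primary ORR as non-responders. Otherwise the supportive analysis could be stricter than the primary one.

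The cost is a few sentences in the SAP and a protocol change at the next amendment, with no new data. Per-protocol ORR and PFS become slightly less favourable.
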